## 8.0 SELECTION AND WITHDRAWAL OF SUBJECTS

This trial will enroll at least 30 eligible subjects for participation to result in 30 evaluable subjects.

### 8.1 Selection Criteria

#### 8.1.1 Inclusion Criteria:

1. Female
2. 18 years of age or older
3. Scheduled to undergo mastectomy or lumpectomy for Invasive Breast Cancer (clinical stage 1 or 2, ER+ low-to intermediate-grade) or DCIS
4. Pathological diagnosis of Invasive Ductal Carcinoma or Ductal Carcinoma *in Situ* (DCIS) requiring mastectomy or lumpectomy (Mixed ductal and lobular carcinoma acceptable)
5. Estrogen Receptor positive biopsy, as determined from a biopsy specimen obtained no more than 3 months prior to entry
6. ECOG performance scale of 0-1 (Appendix A)
7. Adequate organ function as defined by the following criteria:
  - a. Absolute neutrophil count (ANC)  $\geq 1500/\mu\text{L}$
  - b. Platelets  $\geq 100,000/\mu\text{L}$
  - c. Hemoglobin  $\geq 9.0 \text{ g/dL}$
  - d. Creatinine  $\leq 2$  times upper limit of normal

- e. Bilirubin  $\leq$  2 times upper limit of normal
  - f. Transaminases (AST/SGOT and ALT/SGPT)  $\leq$  2.5 times upper limit of normal
8. Able to sign informed consent
  9. Willing to use effective contraception for at least 100 days post study drug administration if subject is pre-menopausal.

#### **8.1.2 Exclusion Criteria:**

1. Concurrent treatment with another anti-estrogen
2. Presence of an active infection requiring systemic therapy.
3. The following conditions contra-indicating fulvestrant administration:
  - a. Subjects with bleeding diatheses, thrombocytopenia or current anticoagulant use (excluding aspirin and anti-inflammatories)
  - b. Subjects with a known hypersensitivity to fulvestrant or any of its formulation components including castor oil, alcohol, benzyl alcohol, and benzyl benzoate.
  - c. Severe hepatic impairment.
4. Prior surgery on the ipsilateral breast which interrupts communication of the ductal systems with the nipple
5. Prior radiation to the breast
6. Pregnant or lactating
7. Impaired cardiac function or history of cardiac problems of NYHA Class III and IV (Appendix C 20.4)
8. Poor nutritional state as indicated by a BMI below 20. -
9. Presence of serious infection not controlled with systemic therapy
10. History of allergies to Lidocaine or Novocain
11. Concurrent participation in an experimental drug study.

#### **8.2 Inclusion of Special Populations**

Only women will be enrolled in this trial; men lack an anatomically accessible duct system. There will not be anyone included under the age of 18 nor will pregnant women participate in this trial. All race and ethnic groups are eligible to participate.

#### **8.3 Determination of Eligibility**

Once the clinician has obtained a signed informed consent, subjects will be registered with the study coordinator and investigator. Additional testing, beyond routine pre-operative testing which may be required to determine eligibility, will be performed. This is outlined below under Section 9.2 Baseline Assessment After eligibility is established, each subject will be assigned a study number to identify them individually. Subjects will not undergo any study related drug administration until eligibility is confirmed with additional testing if necessary and the subject receives a study number.

#### **8.4 Subject Discontinuation**

All subjects have the right to terminate participation in the study at any time. The Investigator also has the right to discontinue the subject's participation at any time

regardless of whether the subject wishes to continue in the study. The Sponsor may discontinue the study at anytime.

In addition, subjects may be withdrawn from the study for the following reasons:

- Occurrence of a clinically unacceptable AE
- Violation of the study protocol or lack of compliance with protocol regimens
- Subject declines further study participation
- Subject withdraws informed consent
- Investigator judges it is in the best interest of the subject

If a subject is withdrawn or discontinues study participation, reasonable efforts will be made to bring the subject in to complete the final study procedures. The subject will continue to be followed and medically managed in accordance with the arrangement that was in place prior to study enrollment. The reason(s) for a subject's discontinuation from the study are to be recorded in the source documentation and on the CRFs.

Any subject, who voluntarily or involuntarily withdraws from the study prior to mastectomy or lumpectomy, will be replaced.

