### **9.9 Subject Early Discontinuation**

Subjects who discontinue after any fulvestrant administration on Day 0 will complete the following procedures.

- Concomitant Medications
- Adverse Events Evaluation
- Reason(s) for discontinuation
- Pregnancy test (for woman of child-bearing potential)

If a subject is withdrawn or discontinues study participation, reasonable efforts will be made to complete the final study procedures. The subject will continue to be followed and medically managed in accordance with the arrangement that was in place prior to study enrollment.

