**Table 2: Schedule of Assessments**

Timeline	Baseline	Fulvestrant Administration	Post Administration		Pre-Op	Day of Surgery	Day of Discharge 	Early Discontinuation
	Day							
Procedures	-14 to -1	0	1 and 2	7 (±2)	14 - 21	DOS (Day 14 to 45)	DOS +	Post fulvestrant administratio
Informed Consent	X							
Registration	X							
Physical Exam	X				X			
Medical History	X							
ECOG Performance Status	X				X			
Vital Signs 	X	X 		X	X		X	
Digital tumor imaging if needed	X				X			
PK - Plasma Fulvestrant Level		X 		X	X			
CBC with Diff & Platelets 	X				X			
Chemistry panel 	X				X			
Pregnancy Test 	X	X			X			X
Pain Assessment		X 		X	X			
Fulvestrant administration		X						
Concomitant Medications	X	X	X 	X	X		X 	X 
Adverse Event Evaluation		X 	X 	X	X		X	X 
Clinical Breast Assessment	X						X	
Pathological Assessment 	X						X	
Reason(s) for Discontinuation								X

1 Blood pressure, pulse, respiration, temperature

2 Prior to fulvestrant administration

3 On Day 0/fulvestrant administration, PK plasma samples are obtained pre-fulvestrant administration, and 4.5 hours post administration (see Table 1)

4 Includes hemoglobin, hematocrit, platelets and white blood cell count with differential

5 Includes Na+, K+, BUN/Urea, serum Cr, Glu, Alb, AST, ALT, Tbili

6 On Day 0/fulvestrant administration Pain Assessment completed prior to fulvestrant administration/nipple preparation (Intraductal only), Post Nipple Anesthesia (Intraductal only), at completion of fulvestrant administration, 30 minute, 1 and 4.5 hours post administration. (see Section 9.10)

7 Assessment by phone is allowed

8 Collection of anesthesia, fluid support or post-surgical pain management is not required

9 Assess adverse events during fulvestrant administration, immediately after administration, at 30 minutes, 1 hour and 4 hours

10 Only women of childbearing potential are tested at baseline or thereafter

11 Includes tissue sample collection for fulvestrant concentration

12 Participation in the trial concludes upon discharge from the hospital

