### **10.1 Pathological Assessment**

The clinic pathologist will conduct the pathologic examinations per institutional standards. Additional instructions are provided by the Sponsor.

The purpose of pathological examination is to provide objective assessment of local effect of fulvestrant on nipple skin, ductal cells (benign and malignant), and surrounding fibroadipose tissues. Specifically, the effect of fulvestrant on cell death (apoptosis and necrosis), proliferation (mitosis), and inflammatory reaction will be examined.

Mastectomy or lumpectomy specimens will be received and processed at the site's laboratory after intramuscular or intraductal therapy per institutional standards. Additional instructions are provided by the Sponsor, to include examination of the tissue for pathological evidence of response. Specific attention will be paid to identify the cannulated ducts. Aided by the colored Hydrogel of mastectomy specimens, the ducts identified in the breast parenchyma will be correlated with duct openings identified on the nipple (with suture), and compare the cannulated ducts (areas) with non- cannulated ducts (areas) for cell death, proliferation, and inflammatory response, as examined using routine hematoxylin and eosin (HE) sections. It is assumed that in most subjects, not every duct will be identified or accessed and in these cases those ducts which are not cannulated will be compared to the ones that were cannulated from a histological stand point. Samples will be stored per site's standard procedures.

A mastectomy or lumpectomy specimen will be dissected and samples taken to measure tissue fulvestrant levels.

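### A subject withdrawn after the Day 0 dose is replaced, and the discontinuation schedule does not call for a study reading of her surgical specimen, so the specimen endpoints could be modestly selected on tolerability

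*Combined protocol and SAP*

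**What the plan says.** Fulvestrant is given once, on Day 0 (Sections 7.0 and 9.3), and surgery follows 14 to 45 days later (Section 9.3.4).

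**Withdrawal and replacement.** Section 8.4 lists among the reasons for withdrawal "Occurrence of a clinically unacceptable AE" and protocol violation. It also lets the investigator stop a subject's participation "regardless of whether the subject wishes to continue in the study". It then states: "Any subject, who voluntarily or involuntarily withdraws from the study prior to mastectomy or lumpectomy, will be replaced". For those who leave, "reasonable efforts will be made to bring the subject in to complete the final study procedures". Section 8.0 sets the target: "This trial will enroll at least 30 eligible subjects for participation to result in 30 evaluable subjects". Neither the final procedures nor evaluability is defined.

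**What is collected after withdrawal.** Section 9.9 opens: "Subjects who discontinue after any fulvestrant administration on Day 0 will complete the following procedures". Its list has four items: concomitant medications, adverse events, the reason for stopping and a pregnancy test. It then repeats the best-efforts clause. Table 2 marks Pathological Assessment at Baseline and Day of Discharge only. Its footnote reads "Includes tissue sample collection for fulvestrant concentration", so tissue sampling is tied to the same marks.

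**What depends on the specimen.** Under Section 13.2, irritation read on the excised tissue is one of three measures of the primary safety endpoint. Ki67 change is the primary efficacy endpoint, and ER and PgR changes are secondary.

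**The concern.** No further dose is due after Day 0, so withdrawing a subject for an adverse event stops observation and not treatment. Her operation and the hospital's own pathology go ahead in any case. Yet the two places written for her situation leave the study reading out, and the replacement rule refills her place.

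The subject withdrawn for local breast toxicity is the one whose irritation reading matters most in a first-step safety study of this route. If she is not read, or is later treated as not evaluable, the irritation rate tends downward. The Ki67 and ER/PgR samples would also lean towards women who tolerated the instillation, although the direction of any effect on those markers is unknown. Because the count is restored, the loss would not show in the number analysed.

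**Working it through.** **1. The plan's own figure.** Section 13.2 gives detectable effect sizes of 0.60 (80% power) and 0.69 (90% power) with 24 intraductal subjects and a paired t-test. The significance level is not stated; I assume 0.05 two-sided. With 23 degrees of freedom and noncentrality d × √24:

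- d = 0.60: noncentrality 2.94, power 80.4%
- d = 0.69: noncentrality 3.38, power 89.9%

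A one-sided test would give 88.6% and 94.9%, so the figures are two-sided. The implied SDs also agree: 50/83.7 = 0.597 and 50/72.3 = 0.692. The stated power reproduces and is not disputed. Replacement keeps n at 24, so the issue is who is in the sample, not how many.

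**2. The text, route by route.**

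| Dosed subject | Specimen reading provided for? |
|---|---|
| Infusion stopped for Grade 3 or 4 pain | Yes, Section 9.11 keeps pathology |
| Surgery postponed for an adverse event | Yes, Section 9.3.4 keeps her in the trial and the analysis |
| Withdrawn for another adverse event or a violation | Not expressly: absent from the Section 9.9 list and from Table 2's Early Discontinuation column; possible through Section 10.1 or the best-efforts clause |

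**3. Irritation rate.** Let x of 24 read specimens show irritation, and let k further dosed subjects be unread. The rate among all dosed lies between x/(24+k) and (x+k)/(24+k), a width of k/(24+k):

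- k = 1: 1/25 = 4.0 points
- k = 2: 2/26 = 7.7 points
- k = 3: 3/27 = 11.1 points

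Five groups of five (Section 9.1) would make 25 intraductal subjects, where Section 13.2 has 24. The widths are then 1/26 = 3.8, 2/27 = 7.4 and 3/28 = 10.7 points.

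For scale, take x = 2. The observed rate is 2/24 = 8.3%, with exact (Clopper-Pearson) 95% interval 1.0% to 27.0%. With k = 3 the possible rates run from 2/27 = 7.4% to 5/27 = 18.5%, all inside that interval. In the worst case, 5/27, the exact interval is 6.3% to 38.1%, so the upper limit moves from 27.0% to 38.1%.

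**4. Ki67.** If the unread differ from the read by d standard deviations of the change, the mean over the 24 read differs from the mean over all dosed by d × k/(24+k) SD. The standard error at n = 24 is 1/√24 = 0.204 SD.

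| k | Shift, d = 0.5 | Shift, d = 1.0 | Shift ÷ standard error |
|---|---|---|---|
| 1 | 0.020 SD | 0.040 SD | 0.10 to 0.20 |
| 3 | 0.056 SD | 0.111 SD | 0.27 to 0.54 |

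The values of k, x and d are my assumptions; only the 24 comes from the plan.

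**The case against.** The best case for the plan is that it leans towards reading these specimens. Section 9.9 gives its short list and then separately asks for efforts to complete the final procedures. If the list were everything, that sentence would be redundant, and the natural candidate is Section 9.8, which includes Pathological Assessment. Section 10.1 has specimens handled at the site's "laboratory after intramuscular or intraductal therapy per institutional standards", examined for response and stored, with no exception for withdrawn subjects. The likeliest tolerability routes are already protected by Sections 9.3.4 and 9.11. Replacement may be ordinary top-up to 30 evaluable subjects. Section 13.0 promises a detailed SAP before database lock, which can set the analysis set. The magnitudes rest on assumed inputs, and irritation has no hypothesis test.

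Much of this stands, and it limits the point to a minor one. It does not close the gap. The final procedures are undefined and best-efforts only. Section 10.1 is a general description that does not say a withdrawn subject's tissue is read for the study or analysed. A SAP can define who is analysed, but it cannot supply a reading that was never collected or consented to. Sampling error appears in a confidence interval; selection on tolerability does not.

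A reader might infer three stronger things, none of which the documents support:

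- *That withdrawn subjects' data are thrown away.* The text says replaced, not discarded.
- *That adverse-event reporting is biased.* The reporting text that follows Section 11.2.6 keeps every intraductally dosed subject in the adverse-event analyses.
- *That every dosed subject belongs in the primary Ki67 analysis.* Another anti-estrogen (barred in Section 9.10) or surgery outside Day 14 to 45 can itself change the marker, so an evaluable set for Ki67 is defensible if it is pre-specified.

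**Conclusion.** The gap is real and minor. As written, a dosed subject withdrawn for an adverse event can be replaced without a study reading of her specimen. Nothing shows that this will happen often, or that any conclusion of the trial would change.

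The effect bears most on the irritation component of the primary endpoint, where the expected direction is downward. It bears less on Ki67 and ER/PgR, where the direction is unknown. For one to three unread subjects it is small beside the sampling error of a 24-subject group. This rests on an assumed number of unread subjects, an assumed difference between read and unread, and an illustrative base rate of 2/24. It also rests on reading the Section 9.9 list and Table 2 as the operative schedule for those who discontinue. If the sponsor intends the final procedures to include Section 9.8 pathology, the remedy is simply to say so. I class this as a cheap improvement.

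**What to change.** - **Section 9.9 and Table 2:** add Pathological Assessment of the routine surgical specimen (irritation, Ki67, ER/PgR), when it becomes available, for every dosed subject who has not withdrawn consent. State that it is part of the final study procedures.
- **Section 8.4:** state that replacements are added to dosed subjects and do not take their place.
- **Irritation summary:** include all dosed subjects with a specimen, and report the number of dosed subjects without a reading.
- **Ki67 and ER/PgR:** include subjects withdrawn for adverse events. Let the SAP pre-specify how to handle violations that affect the marker (other anti-estrogen use, surgery outside Day 14 to 45), with a sensitivity analysis in all dosed subjects who have a reading.

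The cost is a few sentences, one mark and a footnote in Table 2, consent wording for use of the specimen after withdrawal, and a few extra readings. No visit, operation or increase in the target sample size is needed. Biopsy-to-surgery intervals become slightly more variable.

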## 9.0 TREATMENT OF SUBJECTS

### 9.1 Study Related Procedures

After each subject has reviewed and signed the informed consent, she will be enrolled in the study and assigned a study number as outlined below in Section 17.3 Data Collection Requirements. Further testing maybe necessary to determine eligibility and will commence upon enrollment. These tests are included in Section 9.2 Baseline Assessment. Some of the exams, tests or procedures may be a part of routine care for breast cancer and may be used as baseline assessments if conducted no more than 2 weeks prior to participation in the study. Other tests are only being done for the purpose of the study. A member of the study staff will go over, in detail, with each subject the tests that are being done specifically for the study and those that are considered routine care.

All subjects will receive fulvestrant, but the actual total dose received may vary within subjects receiving fulvestrant intraductally, as it is guided by the number of accessible ducts and volume of the ducts.

The first subject of each group will receive intramuscular (IM) fulvestrant (500 mg) and the next five subjects of that group will receive intraductal (ID) fulvestrant up to 500 mg. There are five groups, for a total of 30 subjects. After fulvestrant instillation, both signs and symptoms of local (breast and chest wall) and systemic toxicity will be evaluated using the CTCAE v. 5.0. Each Group – IM; ID, ID, ID, ID, ID.

### 9.2 Baseline Assessment (Day -14 to -1)

Prior to fulvestrant administration, each subject will undergo testing for baseline data collection. Any baseline tests performed within 2 weeks prior to study enrollment need not be repeated: those data will be considered adequate for baseline evaluation.

Baseline tests include all of the following:

- Registration
- Medical History
- ECOG performance Status
- Vital Sign (blood pressure, pulse, respirations, temperature)
- Digital tumor imaging if a recent digital image is not available
- Complete blood count with differential and platelet counts (includes hemoglobin, hematocrit, platelets and white blood cell count with differential)
- Chemistry panel (Includes Na+, K+, BUN/Urea, serum Cr, Glu, Alb, AST, ALT, Tbili)
- Pregnancy test (for women of childbearing potential/pre-menopausal)
- Concomitant Medications
- Clinical Breast Assessment
- Pathological Assessment

If any of these tests or examinations, reveal criteria rendering the subject ineligible, they will be excluded from the study. **All subjects must have at least 14-days between fulvestrant administration and surgery.**

### 9.3 Day of Fulvestrant Administration (Day 0)

The following procedures should be performed on Day 0 fulvestrant administration:

- Vital signs (blood pressure, pulse, respirations, temperature) - prior to fulvestrant administration
- PK - Plasma Fulvestrant Level (see Table 1)
- Pain Assessment (see Section 9.10)
- Concomitant Medications
- Adverse Events
- Pregnancy test of (for women of child-bearing potential/pre-menopausal)

#### 9.3.1 Intramuscular Administration of Fulvestrant

The first subject of each of group will be treated with single dose 500 mg of intramuscular fulvestrant per the prescribing information, (Appendix 20.3) and can also be found at the following website: <http://www.azpicentral.com/faslodex/faslodex.pdf#page=1>

#### 9.3.2 Intraductal Administration of Fulvestrant

The second through sixth (2nd through 6th) subject of each of 5 groups will receive intraductally administered fulvestrant Jabczenski Ductogram Cannula Microcatheter, the IntrocanSafety IV Catheter or other catheter suitable to delivery fulvestrant to the milk ducts. Fulvestrant will be infused in up to 5 breast ducts of the breast containing DCIS or invasive cancer. Ducts infused with fulvestrant will be marked with sutures. If sutures cannot be maintained until mastectomy or lumpectomy, other methods should be employed to mark the ducts, as specified in the instruction manual. At least one photograph of the breast documenting infusion location should be taken for the CRF. Do not instill more than 10 mL (500 mg) (i.e., the maximum delivered dose is never to exceed the dose currently in routine clinical use for intramuscular delivery). Detailed instructions for intraductal fulvestrant

administration and use of devices are located in the administration manual provided and will be performed on the intraductal fulvestrant subjects only.

### 9.3.3 Plasma Drug Concentration Levels

Subjects will have blood drawn two times on the day of intraductal administration of fulvestrant to determine plasma concentration levels. Table 1 lists the sampling schedule (below).

**Table 1: PK - Plasma Fulvestrant Level Schedule**

PK - Plasma Fulvestrant Level Blood Draw Schedule (Intramuscular and Intraductal)
Pre-fulvestrant – single blood sample for baseline
Post fulvestrant administration:

• 4.5 hours, Subjects are discharged following the 4.5 hour blood collection

• Day 7

• Pre-surgery

### 9.3.4 Post Fulvestrant Administration and Pre-Surgery Assessment

After fulvestrant administration has been completed, subjects will be assessed for local and systemic adverse events during, immediately after and at 30 minutes, 1 hour and 4 hours. As noted above, **subjects must have at least 14 days between fulvestrant administration and surgery, but no longer than 45 days.** Pre-operative assessment, as described below, will occur before the subject undergoes mastectomy or lumpectomy 14 days following intraductal therapy, unless medical condition prohibits operative management. Subjects will complete a pain assessment at completion of fulvestrant administration, then at 30 minutes, 1 hour, and 4.5 hours until discharge from the clinic. Following discharge, the site trial staff may assess for AEs by phone. Subjects will be assessed for pain, AE, ECOG performance scale (Appendix A), blood drawn per drug schedule and vital signs (blood pressure, respiratory rate, pulse, temperature) recorded. See Table 2 to determine daily requirements for study procedures.

Subjects participating in this clinical trial will undergo either a mastectomy or lumpectomy. Notwithstanding the unlikely occurrence of an AE that affects the surgery date, participation in this trial does not alter the scheduled surgical management of mastectomy/lumpectomy or date. In order for subjects to undergo surgery, Atossa recommends but does not require the following requirements be met:

- ECOG performance scale of 0-2
- Stable vital signs (pulse, blood pressure, respiratory rate and temperature)
- Adequate organ function as determined by:
  - Absolute neutrophil count (ANC)  $\geq 1500/\mu\text{L}$
  - Platelets  $\geq 100,000/\mu\text{L}$
  - Hemoglobin  $\geq 9.0 \text{ g/dL}$
  - Creatinine  $\leq 2$  times upper limit of normal
  - Bilirubin  $\leq 2$  times upper limit of normal
  - Transaminases (AST/SGOT and ALT/SGPT)  $\leq 2.5$  times upper limit of normal

The surgeon may elect to postpone the surgery if adverse events may compromise patient

safety. In the event this occurs, subjects will be treated to abate adverse events prior to surgery. They will remain in the clinical trial and be included for analysis.

